### 4.2 Secondary Endpoints

The secondary endpoints for this study include:

#### 4.2.1 Efficacy Endpoints

- Absolute change from Induction 1 (baseline visit) to Induction 2 (visit 7, Week 4) in plasma epinephrine concentration after 30 minutes of induced hypoglycemia with PG <50 mg/dL. The average of the non-missing results at each step will be used in analysis.
- Percent change from Induction 1 (baseline visit) to Induction 2 (visit 7, Week 4) in plasma epinephrine concentration after 30 minutes of induced hypoglycemia with PG <50 mg/dL by Diabetes Duration Category (<15 years, ≥15 years). The average of the non-missing results at each step will be used in analysis.
- Intravenous glucose infusion rate (GIR) [time frame: 0-30 mins induced hypoglycemia] (cumulative glucose infusion rate required to maintain insulin-induced hypoglycemia).
- Intravenous insulin infusion rate [time frame: 0-30 mins induced hypoglycemia] (cumulative insulin infusion rate required to maintain insulin-induced hypoglycemia).
- Change from Induction 1 (baseline visit) to Induction 2 (visit 7, Week 4) in other counter regulatory hormones (norepinephrine, glucagon, cortisol and growth hormone plasma concentrations) after 30 mins of induced hypoglycemia.
- Change from Induction 1 (baseline visit) to Induction 2 (visit 7, Week 4) in Neuroglycopenic Symptom Scores (if hypoglycemia present) as documented using the hypoglycemia symptom questionnaire.
- Change from Induction 1 (baseline visit) to Induction 2 (visit 7, Week 4) in Autonomic Symptom Scores (if hypoglycemia present) as documented using the hypoglycemia symptom questionnaire.
- Change from baseline to Week 4 in CGM-derived hypoglycemia parameters of:
  - Proportional time spent with interstitial glucose (IG) <70, 60, and 50 mg/dL;
  - Rate of hypoglycemic event episodes at thresholds of plasma glucose <70, 60, and 50 mg/dL.
  - Area over the curve (AOC) of the reduction from baseline in the interstitial glucose from T0 (defined as the date/time of the CSGI injection) to Tx, where x corresponds to time when interstitial glucose < 70, <60 and <50 mg/dL is achieved.
- Change from baseline to Week 4 in CGM-derived parameters of:
  - Average interstitial glucose and standard deviation;
  - Proportional time within  $70 \leq \text{interstitial glucose} < 180$  mg/dL;

- Proportional time with interstitial glucose  $\geq 180$  mg/dL.
- Change from Induction 1 (baseline visit) to Induction 2 (visit 7, Week 4) in the Gold scale as a measure of hypoglycemia awareness.

#### **4.2.2 Safety and Tolerability Endpoints**

- Safety-related parameters including:
  - Reported hypoglycemic events;
  - Insulin dose (adjustments during the study);
  - Vital signs;
  - Physical exam;
  - ECG;
  - Standard safety laboratory parameters;
  - Incidence of adverse events (AEs) and serious adverse events (SAEs);
  - Subjective injection site discomfort as reported by subjects using a 100-mm VAS and other questionnaires;
  - Erythema and/or edema formation at site of injection assessed by an investigator using the modified Draize scale.

#### **4.2.3 Immunogenicity Endpoints**

- Plasma glucagon and serum glucagon antibodies;

### **5 SAMPLE SIZE**

The primary hypothesis is to evaluate change from Induction 1 (baseline visit) to Induction 2 (visit 7, Week 4) in plasma epinephrine concentration after 30 minutes of induced hypoglycemia with plasma glucose  $< 50$  mg/dL between treatment groups. Sample size is based on a closed hierarchical hypothesis test. Using this method, an alpha of 5% will be preserved for each hypothesis test where the next ordered test will only be conducted if statistical significance is achieved for that hypothesis.

Final calculations are based on 80% power and an alpha of 5%, to demonstrate a plasma epinephrine increase compared to placebo of 1.5 nmol/l given a SD of 1.34 nmol/l at an induced PG of 50 mg/dl. Sixteen subjects per treatment group (CSGI high dose, CSGI low dose, and placebo) are required based on the minimum sample size estimate for a comparison.

### **6 RANDOMIZATION**

The randomization scheme is 1:1:1 for high dose, low dose and placebo. Each group will have 16 subjects, but the placebo group will be matched to high and low infusion rates (8 in each group). The randomization is stratified by site.

### **7 PLANNED ANALYSES**

No statistical analysis plan (SAP) prepared in advance of the data can be absolutely definitive and the final clinical study report (CSR) may contain additional tables or statistical tests if warranted by the data obtained. The justification for any such additional analyses will be fully documented in the final CSR.

## **7.1 Analysis Populations**

Subjects excluded from the analysis sets and the reason for their exclusion will be listed in Appendix 16.2. Enrolled subjects are subjects that have signed ICF, been assigned a subject number and randomized.

### **7.1.1 Intent-to-treat Population (ITT or All Randomized)**

The ITT population includes all randomized subjects. The ITT population will be analyzed according to the treatment group to which subjects were randomized.

ITT population will be used for primary and secondary efficacy endpoints.

### **7.1.2 Per-Protocol Population (PP Population)**

The PP population will be a subset of the ITT population consisting of those subjects who:

- Satisfy all of the inclusion/exclusion criteria;
- Participate in the study through day 27 with no major protocol deviations

All protocol deviations will be assessed and documented on a case-by-case basis before the database lock, and deviations considered to have a serious impact on the efficacy results will lead to the relevant subject being excluded from the PP population. Before database lock, potential subject exclusions from PP population will be reviewed by the Sponsor and documented in a subject evaluability document.

PP population will be used for sensitivity analysis of the primary efficacy endpoint.

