## 7.5 Protocol Deviations

Protocol deviations will be identified during blinded data review by Sponsor and Medical Monitor and classified as major or minor. Subjects with major protocol deviations will be excluded from PP population..

The number of subjects with major and minor protocol deviations will be summarized descriptively with counts and percentages for ITT population and listed.

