### **8 INTERIM ANALYSIS**

No interim analyses are planned. However, the primary endpoint analysis at Day 27 will be executed when the last subject data for this visit has been completed and monitored. Primary endpoint analysis results will only be unblinded at the treatment group level (CSGI high dose, CSGI low dose, placebo) and individual treatment assignments will remain blinded until the end of the study and the final database locked. Study investigators, study staff, subjects and the sponsor will remain blinded to individual group assignments. Primary endpoint analysis is defined as all analyses that include the evaluation of epinephrine (both primary and secondary designated analyses) and other corresponding counter regulatory hormones (norepinephrine, cortisol, glucagon and growth hormone).

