## 12 LIST OF TABLES, FIGURES AND LISTINGS

The following table includes details of the tables, figures and listings (TFLs) for the study. Those marked with an asterisk (\*) are planned for the primary endpoint analysis and presentation of the accompanying safety analysis for that time period (See Section 8).

Table Number	Table Title	Shell Number (if repeat)
14.1.1.1*	Summary of Subject Disposition - All Subjects	
14.1.1.2*	Summary of Analysis Populations - All Randomized Subjects	
14.1.2*	Summary of Protocol Deviations - Intent-to-Treat Population	
14.1.3.1*	Summary of Demographic and Baseline Characteristics - Safety Population	
14.1.3.2*	Summary of Demographic and Baseline Characteristics - Intent-to-Treat Population	14.1.3.1
14.1.3.3*	Summary of Demographic and Baseline Characteristics - Per Protocol Population	14.1.3.1
14.1.4*	Summary of Medical History - Intent-to-Treat Population	
14.2.1.1*	Percent change from Induction 1 (Baseline visit) to Induction 2 (Visit 7, Week 4) in Plasma Epinephrine Concentration During Induced Hypoglycemia with PG <50 mg/dl Intent-to-Treat Population	
14.2.1.2*	Percent change from Induction 1 (Baseline visit) to Induction 2 (Visit 7, Week 4) in Plasma Epinephrine Concentration During Induced Hypoglycemia with PG <50 mg/dl Per Protocol Population	14.2.1.1
14.2.1.3*	Percent change from Induction 1 (Baseline visit) to Induction 2 (Visit 7, Week 4) in Plasma Epinephrine Concentration During Induced Hypoglycemia with PG <50 mg/dl, Sensitivity analysis 1* Per Protocol Population	14.2.1.1
14.2.1.4*	Percent change from Induction 1 (Baseline visit) to Induction 2 (Visit 7, Week 4) in Plasma Epinephrine Concentration During Induced Hypoglycemia with PG <50 mg/dl, Sensitivity analysis 2* Per Protocol Population	14.2.1.1
14.2.1.5*	Percent change from Induction 1 (Baseline visit) to Induction 2 (Visit 7, Week 4) in Plasma Epinephrine Concentration During Induced Hypoglycemia with PG <50 mg/dl, Sensitivity analysis 3* Per Protocol Population	14.2.1.1
14.2.2.1.1*	Absolute change from Induction 1 (Baseline visit) to Induction 2 (Visit 7, Week 4) in Plasma Epinephrine Concentration During Induced Hypoglycemia with PG <50 mg/dl Intent-to-Treat Population	14.2.1.1

Table Number	Table Title	Shell Number (if repeat)

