14.2.2.1	Cumulative Glucose Infusion Rate (GIR) Required to Maintain Insulin-Induced Hypoglycemia Over Time - Intent-to-Treat Population	
14.2.2.2	Cumulative Glucose Infusion Rate (GIR) Required to Maintain Insulin-Induced Hypoglycemia Over Time - Per Protocol Population	14.2.2.1
14.2.3.1	Cumulative Insulin Infusion Rate Required to Maintain Insulin-Induced Hypoglycemia Over Time - Intent-to-Treat Population	14.2.2.1
14.2.3.2	Cumulative Insulin Infusion Rate Required to Maintain Insulin-Induced Hypoglycemia Over Time - Per Protocol Population	14.2.2.1
14.2.4.1.1	Average Neuroglycopenic Scores (ANS), Average Autonomic Scores (AAS) and Average Total Scores (ATS) with PG <70 mg/dl Over Time - Intent-to-Treat Population	
14.2.4.1.2	Average Neuroglycopenic Scores (ANS), Average Autonomic Scores (AAS) and Average Total Scores (ATS) with PG <70 mg/dl Over Time - Per Protocol Population	14.2.4.1.1
14.2.4.2.1*	Average Neuroglycopenic Scores (ANS), Average Autonomic Scores (AAS) and Average Total Scores (ATS) with PG <50 mg/dl Over Time - Intent-to-Treat Population	14.2.4.1.1
14.2.4.2.2*	Average Neuroglycopenic Scores (ANS), Average Autonomic Scores (AAS) and Average Total Scores (ATS) with PG <50 mg/dl Over Time - Per Protocol Population	14.2.4.1.1
14.2.5.1.1	CGM-Derived Hypoglycemia Parameters by Day - Intent-to-Treat Population	
14.2.5.1.2	CGM-Derived Hypoglycemia Parameters by Day - Per Protocol Population	14.2.5.1.1

Figure Number	Figure Title	Shell Number (if repeat)
14.2.5.2.1	CGM-Derived Hypoglycemia Parameters by Week - Intent-to-Treat Population	14.2.5.1.1
14.2.5.2.2	CGM-Derived Hypoglycemia Parameters by Week - Per Protocol Population	14.2.5.1.1
14.2.6.1	Gold Scale Assessment of Hypoglycemia Unawareness Over Time - Intent-to-Treat Population	
14.2.6.2	Gold Scale Assessment of Hypoglycemia Unawareness Over Time - Per Protocol Population	14.2.6.1

Listing Number	Listing Title	Shell Number (if repeat)
16.1.7*	Randomization of Subjects Intent-to-Treat Population	
16.2.1.1*	Subject Disposition All Subjects	
16.2.1.2*	Subject Eligibility and Inclusion/Exclusion Criteria Assessment All Subjects	
16.2.2.1*	Protocol Deviations All Subjects	
16.2.2.2	Major Protocol Deviations All Subjects	
16.2.3*	Analysis Populations All Randomized Subjects	
16.2.4.1*	Subject Demographic and Baseline Characteristics Intent-to-Treat Population	
16.2.4.2*	Medical History Intent-to-Treat Population	
16.2.4.3*	Prior and Concomitant Medications Safety Population	

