16.2.5.1	Study Drug Administration Intent-to-Treat Population	
16.2.5.2	Euglycemic Baseline and Hypoglycemia Induction Intent-to-Treat Population	
16.2.5.3*	Plasma Blood Glucose during Euglycemic Maintenance, Hypoglycemia Induction and Stabilization, and Normalization to Euglycemia All Subjects	
16.2.5.4	Plasma Blood Glucose Levels from Plasma Glucose Screener Intent-to-Treat Population	
16.2.6.1	Subject Insulin Diary Safety Population	
16.2.6.2.1	Interstitial Glucose Parameters During CGM Monitoring All Subjects	
16.2.6.3.1	Average Glucose Infusion Rate to Maintain Glucose at 50 mg/dL for the first 30 minutes after 50 mg/dL Achieved during Hypoglycemia Stabilization All Subjects	
16.2.6.3.2	Cumulative Glucose Infusion to Maintain Glucose at 50 mg/dL for the first 30 minutes after 50 mg/dL Achieved during Hypoglycemia Stabilization All Subjects	
16.2.6.4.1.1	Hypoglycemia Symptom Questionnaire Responses After Achieving Plasma Glucose of < 70 mg/dL All Subjects	
16.2.6.4.1.2*	Hypoglycemia Symptom Questionnaire Responses After Achieving Plasma Glucose of < 50 mg/dL All Subjects	

Listing Number	Listing Title	Shell Number (if repeat)
16.2.6.4.2.1	Average Neuroglycopenic, Autonomic and Total Symptom Scores After Achieving Plasma Glucose of < 70 mg/dL All Subjects	
16.2.6.4.2.2*	Average Neuroglycopenic, Autonomic and Total Symptom Scores After Achieving Plasma Glucose of < 50 mg/dL All Subjects	
16.2.6.4.3.1	Overall Assessment of Hypoglycemia After Achieving Plasma Glucose of < 70 mg/dL All Subjects	
16.2.6.4.3.2	Overall Assessment of Hypoglycemia After Achieving Plasma Glucose of < 50 mg/dL All Subjects	
16.2.6.4.4	Gold Scale of Hypoglycemia Unawareness All Subjects	
16.2.7*	Adverse Events All Patients	
16.2.8.1*	Hormones and Counter Regulatory Hormone Response All Patients	
16.2.8.2	Serum Concentration of Glucagon during CSGI Treatment All Patients	
16.2.8.3	Serum and Plasma Concentration of Glucagon Antibodies All Patients	
16.2.8.4	Clinical Laboratory Results: Hematology All Patients	
16.2.8.5	Laboratory Results: Chemistry, Complete Metabolic Panel Safety Population	
16.2.8.6	Laboratory Results: Drug Screen All Patients	
16.2.8.7	Listing of Laboratory Results: Serology Intent-to-Treat Population	
16.2.8.8	Urine Pregnancy Test Results All Patients	
16.2.9.1	Injection Site Discomfort - Visual Analog Scale (VAS) Safety Population	

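### The SAP lets Per-Protocol membership change after the Week 4 group results are released, and it stars a randomization listing for Week 4 that contradicts the individual blind

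*SAP*

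**What the plan says.** **Who is in the set.** SAP 7.1.2 puts a randomized subject in the Per-Protocol population if all eligibility criteria are met and the subject takes part through day 27 without a major deviation. Deviations are judged case by case, and those thought to affect efficacy results seriously lead to exclusion. The timing is: "Before database lock, potential subject exclusions from PP population will be reviewed by the Sponsor and documented in a subject evaluability document".

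**How deviations are classified.** SAP 7.5: "Protocol deviations will be identified during blinded data review by Sponsor and Medical Monitor and classified as major or minor". It gives no date for this review.

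**When results appear.** Under SAP 8 the Week 4 primary endpoint analysis is "executed when the last subject data for this visit has been completed and monitored". Results are released by treatment group, while "individual treatment assignments will remain blinded until the end of the study and the final database locked".

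**What is produced then.** SAP 12 marks with an asterisk the outputs that "are planned for the primary endpoint analysis and presentation of the accompanying safety analysis for that time period". They include Per-Protocol tables and figures, Listing 16.1.7 ("Randomization of Subjects Intent-to-Treat Population") and Listing 16.2.8.1 ("Hormones and Counter Regulatory Hormone Response All Patients").

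**What the set is for.** SAP 7.1.2 and 7.10.3 use it for the sensitivity analyses of the primary endpoint. SAP 7.1.1 assigns the primary and secondary efficacy endpoints to ITT.

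**The concern.** Exclusion from the Per-Protocol set turns on a judgement about impact on efficacy, with no list of qualifying deviations. The sponsor makes that judgement. Such a criterion should be applied before anyone making it has seen efficacy results. As dated, it can be applied or revisited afterwards, when the arm results are known and each subject's hormone values have been listed.

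The robustness evidence for the primary endpoint is what is exposed. All three planned sensitivity analyses are in the Per-Protocol population and none is in ITT, so a change in membership after Week 4 would alter every one of them.

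The second matter is separate. If Listing 16.1.7 is issued at Week 4 as marked, subject-level assignments would be available while the 3- and 6-month assessments are still running under a blind that SAP 8 says is intact.

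**Working it through.** The plan gives no figure on this point to reproduce. The check is a count of outputs, a comparison of dates, and a reading of the timing text side by side.

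**1. Per-Protocol outputs due at Week 4 (SAP 12).**
- Starred tables naming the Per Protocol population: 14.1.3.3, 14.2.1.2, 14.2.1.3, 14.2.1.4, 14.2.1.5, 14.2.2.1.2, 14.2.2.2.2, 14.2.2.3.2, 14.2.2.4.2, 14.2.2.7.2.2 and 14.2.2.10.2. That is 11 of the 18 Per-Protocol tables.
- Starred figures: 14.2.1.2 and 14.2.4.2.2. That is 2 of the 8 Per-Protocol figures.
- Total: 11 + 2 = 13.
- Reporting epinephrine or another counter-regulatory hormone: tables 14.2.1.2 to 14.2.1.5 (4), tables 14.2.2.1.2, 14.2.2.2.2, 14.2.2.3.2 and 14.2.2.4.2 (4), and figure 14.2.1.2 (1). Total: 4 + 4 + 1 = 9.
- The other 13 − 9 = 4 cover baseline characteristics, symptom scores (one table, one figure) and the Gold scale.
- The three sensitivity analyses are Tables 14.2.1.3 to 14.2.1.5. All are starred.

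**2. Does any text freeze the set before those outputs?**

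| Place | What it fixes | What it leaves open |
|---|---|---|
| SAP 7.1.2 | Review and documentation before database lock | No link to Week 4 |
| SAP 7.5 | Deviation review is blinded | No date; nothing on access to hormone results |
| SAP 8 | Week 4 analysis starts on completed and monitored data | No lock at Week 4; only the final lock is named |
| SAP 12 | Tables 14.1.1.2 and 14.1.2 and Listings 16.2.2.1 and 16.2.3 (populations and deviations) are starred | Records the set at Week 4; does not make it final |

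The Week 4 outputs need a Per-Protocol flag and a classification of deviations, so a first version will exist and be recorded. No sentence prevents a second version.

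**3. How long the set can stay open.** The interval from a subject's Visit 7 to Visit 11 depends on which protocol text is followed.
- Counted from randomization (protocol 9.5): 26 − 4 = 22 weeks; 22 / 4.35 = 5.1 months.
- Counted from the end of treatment (protocol 7.1): 26 weeks; 26 / 4.35 = 6.0 months.
- Visit 11 carries a window of ±1 week in either case.

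The interval that matters runs from sight of the Week 4 results to the lock. It is the figure above, minus the time needed to complete, monitor and report the Week 4 data, plus the time from the last Visit 11 to the lock. The documents give neither time.

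**4. Listing 16.1.7 against SAP 8.** By its title the listing gives the randomization of subjects, and its asterisk schedules it for Week 4. SAP 8 keeps individual assignments blinded to the end of the study and the final lock, for investigators, study staff, subjects and the sponsor. Both cannot be followed as written.

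**The case against.** The strongest reply is that the plan already contains most of the protection.

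- **The review is blinded.** SAP 7.5 says so, and SAP 8 keeps the sponsor blind to individual assignments. Group results alone do not show which arm a given subject is in, so they do not show which exclusion would help. This stands and lowers the risk. It is incomplete: the review has no date, nothing withholds hormone results from it, and Listing 16.1.7 as starred would remove the protection.
- **The Week 4 set is recorded.** Starred Tables 14.1.1.2 and 14.1.2 and Listings 16.2.2.1 and 16.2.3 document populations and deviations, so a later reclassification would show as a difference between the Week 4 and final outputs. This also stands. It makes a change visible but does not prevent it.
- **Membership rests on conduct through day 27.** Later follow-up therefore creates no new relevant events. This is true, and it is also why the set can be closed at Week 4. What can still change is the discovery or the grading of an earlier deviation.
- **The word 'final' implies an earlier lock.** Protocol 11.5 has the parallel sentence without that word, so its addition in SAP 8 may hint at a Week 4 lock. Equally, the protocol's wording suggests that database lock means the end-of-study lock. No earlier lock is defined. If one was intended, the fix only writes it down.
- **The asterisk on 16.1.7 may be a slip.** That is plausible, and SAP 12 does not say who receives the listing. The conflict in the text still needs correcting.

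A reader might also infer that the SAP leaves subjects with a confounding medication to the sponsor's discretion, because protocol 11.1.2 mentions such use and SAP 7.1.2 does not. The documents do not support that reading. SAP 7.1.2 excludes only for failed eligibility or a major deviation. Protocol 8.10 permits medically necessary changes before week 4 and prohibits no medication beyond those in the exclusion criteria. A permitted change is therefore not a deviation, and the subject stays in the set. The clause in protocol 11.1.2 is garbled and, taken literally, counts such use as included.

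**Conclusion.** The gap is real but limited. Per-Protocol membership has no closing date before the Week 4 results, although 13 Per-Protocol outputs, 9 of them on hormones, are produced then and all three planned sensitivity analyses depend on it. Separately, starring Listing 16.1.7 contradicts the individual blind during follow-up.

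The effect is confined to supportive Per-Protocol analyses and to the follow-up blind. The primary ITT analysis is unchanged. If no subject is reclassified after Week 4, the effect on Per-Protocol results is zero. No bias or power figure can be attached, because the documents give no frequency of late reclassification.

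The documents do not show that anyone intends to revise the set, or that the deviation review is in fact unblinded. The 5 to 6 months is an approximate bound on the follow-up interval, subject to the two unstated times above, and is not a measured exposure.

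The conclusion assumes that database lock in SAP 7.1.2 means the lock named in SAP 8, and that Listing 16.1.7 shows each subject's assignment as its title indicates. This is a change to consider, not a flaw in the primary analysis.

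**What to change.** **(a) SAP 7.1.2.** Replace the sentence on the sponsor's review with:

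> *Per-Protocol membership will be decided under the blinded review of Section 7.5, without access to treatment assignment or hormone results, and documented in the signed subject evaluability document before the Week 4 outputs are run; it will not be changed afterwards, and deviations found later will be listed.*

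The sentence before it, which has deviations assessed up to database lock, can stay, because the new sentence settles what later findings may affect.

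**(b) SAP 12.** Remove the asterisk from Listing 16.1.7. As a check when doing so: SAP 7.3.2 mentions treatment groups in the ordering of listings, so confirm from the shells that no other starred by-subject listing prints the arm.

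No medication rule, drug list or entry in SAP 10 on medication is needed.

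**Cost.** One sentence and one asterisk, with no protocol change, new data or new table. The evaluability document already exists in the plan and needs information only through day 27. The downside is that a deviation found by monitoring after Week 4 no longer changes the Per-Protocol set. It is listed instead, and can be shown in a rerun labelled post hoc.
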